10.4. Reporting of Device Deficiencies

Device deficiency (DD) information will be collected throughout the study and are to be reported to Medtronic, as per Table 9: Device Deficiency Reporting Requirements. A Medtronic representative will review the device deficiency for completeness and accuracy and when necessary will request clarification and/or additional information from the Investigator. Note that device deficiencies that result in an adverse device effect (ADE) to the subject should be captured as an Adverse Event only.

Device deficiencies that did not lead to an AE, but could have led to a Serious Adverse Device Effect (SADE) (i.e., if suitable action had not been taken, if intervention had not been made, or if the circumstances had been less fortunate) require immediate reporting. For device deficiencies that require immediate reporting, initial reporting may be done by contacting the study sponsor per the sponsor contact information.

Table 9: Device Deficiency Reporting Requirements

Device Deficiencies and SADE Potential	
Investigator submit to:	
Medtronic	All geographies: Report, without unjustified delay, all device deficiencies that could have led to a serious adverse device effect
Regulatory authorities	All geographies: Submit per local reporting requirement.
IRB/REB/MEC	All geographies: Submit per local reporting requirement.
Sponsor submit to:	
IRB/REB/MEC	All geographies: Submit per local reporting requirement.
Regulatory authorities	
Canada: Any Device Deficiency that:
 
 has resulted in any of the consequences characteristic of an SAE on the patient, the user or any other person; These must be reported by Medtronic within 10 days from the date Medtronic becomes aware. or could do so were it to reoccur. These must be reported by Medtronic within 30 days from the date Medtronic becomes aware. 
Preliminary and final reporting to the Canadian Ministry of Health (Health Canada) of events occurring inside (always) or outside Canada (in case of corrective actions) that is related to a failure of the device or a deterioration in its effectiveness, or any inadequacy in its labeling or its directions for use and has led to the death or a serious deterioration in the state of health of a patient, user or other person or could do so were it to recur. Report a) within 10 days after awareness, if incident has led to death or a serious deterioration in the state of health of a patient, user or other person b) within 30 days, if incident has not led to death or a serious deterioration in the state of health of a patient, user or other person, but could do so were it to recur c) as soon as possible, if incident occurred outside of Canada and is related to a corrective action. (Canada Medical Devices Regulations, SOR/98-282; Mandatory Problem Reporting 59(1), 59(2), 60 (1)).

	All geographies: Submit per local reporting requirement.
All Other Device Deficiencies	
Investigator submit to:	
Medtronic	All geographies: Submit in a timely manner after the Investigator first learns of the event.
IRB/REB/MEC	All geographies: Submit per local reporting requirement.
Regulatory authorities	All geographies: Submit per local reporting requirement.

10.5. Reporting of Product Complaints

In geographies where devices are market-released, product complaint reporting is applicable. This includes when an AE is related to a market-released device during the study. The reporting of product complaints is not part of the Study and should be done in addition to the Adverse Event reporting requirements. Refer to local regulations for reporting requirements.

Product Complaint: Any written, electronic or oral communication that alleges deficiencies related to the identity, quality, durability, reliability, safety, effectiveness or performance of a medical device that has been placed on the market.

It is the responsibility of the Investigator to report all product complaint(s) associated with a market-released medical device distributed by Medtronic, regardless whether they are related to intended use, misuse or abuse of the product. Reporting must be performed immediately and via the regular channels for market-released products.

Medtronic will notify the regulatory authorities (e.g. FDA, Health Canada) as applicable for the following incidents immediately upon learning of them:

- Any malfunction or deterioration in the characteristics and/or performance of a device, as well as any inadequacy in the labeling or instructions for use which led or might have led to the death or serious deterioration in the state of health of a patient, user, or other person.
- Any technical or medical reason resulting in withdrawal of a device from the market by the manufacturer.
- A serious deterioration in the state of health includes:
 - Life-threatening illness or injury
 - Permanent impairment of a body function or permanent damage to a body structure
 - A condition necessitating medical or surgical intervention to prevent permanent impairment of a body function or permanent damage to a body structure

11. Clinical Events Committee

An independent Clinical Events Committee (CEC) will review and adjudicate all adverse events as well as all deaths for subjects participating in the study.

The CEC will consist of a minimum of three (3) non-Medtronic employed physicians that are not participating Investigators for the study, including a CEC chairperson. Medtronic personnel may facilitate and participate in a CEC meeting but will be non-voting members.

For adverse events and deaths reviewed by the CEC, Medtronic will provide the CEC with the Investigator's description and classification. The CEC is responsible for reviewing the Investigator's assessment and supportive documentation (when available), reviewing applicable definitions, and determining final classifications for all adjudication parameters. Additionally, the CEC will provide an adjudication of the death classification for all reported deaths including primary cause of death and cardiac classification.

If the CEC disagrees with the Investigator's classification of the event, the rationale will be provided to the Investigator. If the Investigator agrees with the CEC's adjudication, the eCRF documenting the event will be updated accordingly.

If the Investigator does not agree with the CEC's adjudication classification, both determinations will be provided within the final report; however, the CEC's adjudication will be used for data analysis. The disagreement will also be included in reporting to IRB/REB/MECs and regulatory authorities, if required.

12. Statistical Design and Methods

A separate Statistical Analysis Plan (SAP) will be developed to further describe statistical methods, pre-specified data handling rules, and pre-specified analyses that will be included in study reports. Any deviation from the pre-specified statistical analyses will be noted in the study report.

Additional exploratory analyses of the data may be conducted as deemed appropriate.

As this is a feasibility study, analysis of accruing data will be allowed. Analyses are planned at the following time points (though only select objectives may be analyzed at the first analysis):

- After completion of the 15 subject index procedures and 1 week follow-up visit
- After all subjects have completed follow-up visits through at least the 6 month follow-up visit and have been exited from the study

12.1. Primary Objective

Estimate the incidence of ArcticLine Catheter-related and ArcticLine cryoablation procedure-related serious adverse events (SAEs) with an onset date within 7 days post-procedure.

Endpoint Definition

ArcticLine Catheter-related or ArcticLine cryoablation procedure-related SAEs, with an onset date within 7 days post-procedure (except as noted below), as adjudicated by the Clinical Events Committee (CEC), described as follows:

- Atrioesophageal fistula*
 - * Includes atrioesophageal fistula with an onset date at any time after the study cryoablation procedure and is adjudicated by the CEC as either ArcticLine Catheter-related or ArcticLine cryoablation procedure-related.
- Cardiac perforation/tamponade
- Cerebrovascular accident
- Death
- Esophageal injury
- Major bleeding
- Myocardial infarction
- Pericarditis
- Phrenic nerve injury (ongoing at hospital discharge)
- Transient ischemic attack
- Vagal nerve injury resulting in esophageal dysmotility or gastroparesis
- Vascular access complications

Sample Size

The sample size of 15 treated subjects for this study was chosen with the goal to collect preliminary safety and effectiveness data on the ArcticLine Catheter's use in both the left and right atrium.

Analysis Methods

The percentage of catheter related and cryoablation procedure related SAEs will be calculated as the number of procedures with at least one SAE meeting the endpoint definition divided by the number of cryoablation procedures. Each procedure will count, so subjects with repeat cryoablations will contribute more than once to the denominator. Exact methods will be used to construct a 95% confidence interval for the percentage of procedures with an SAE.

Determination of Patients for Analysis

All ArcticLine cryoablation procedures will be included. An ArcticLine cryoablation procedure is considered to have occurred once the ArcticLine Catheter is introduced into the vasculature.

12.2. Ancillary Objective #1

Estimate the percentage of patients with acute treatment success of the ArcticLine Catheter at the left atrial roof and posterior wall in patients with demonstrated entrance block of all pulmonary veins and who underwent roof and posterior wall ablation with ArcticLine.

Endpoint Definition

Subjects must have confirmed block at the roof line and posterior wall line ("roof/wall") via periprocedural assessment of posterior wall isolation at the completion of the cryoablation procedure to be considered an acute treatment success.

Analysis Methods

The percentage of acute roof/wall treatment successes will be calculated as the number of roof/wall procedures achieving success divided by the number of index ArcticLine cryoablation procedures where the roof/wall was attempted. Exact methods will be used to construct a 95% confidence interval for the percentage.

Determination of Patients for Analysis

All subjects undergoing an ArcticLine cryoablation procedure of the roof/wall will be included. An ArcticLine cryoablation procedure of the roof/wall is considered to have occurred once an ArcticLine cryoapplication at the roof and/or wall begins. Only the first ArcticLine cryoablation procedure of the roof/wall per subject will be included.

12.3. Ancillary Objective #2

Estimate the percentage of patients with acute treatment success of the ArcticLine Catheter at the mitral isthmus in patients who underwent mitral isthmus ablation with ArcticLine.

Endpoint Definition

Subjects must have confirmed bi-directional conduction block at the mitral isthmus line via periprocedural assessment at the completion of the cryoablation procedure to be considered an acute treatment success.

Analysis Methods

The percentage of acute mitral isthmus line treatment successes will be calculated as the number of mitral isthmus line procedures achieving success divided by the number of index ArcticLine cryoablation procedures where the mitral isthmus line was attempted. Exact methods will be used to construct a 95% confidence interval for the percentage.

Determination of Patients for Analysis

All subjects undergoing an ArcticLine cryoablation procedure of the mitral isthmus will be included. An ArcticLine cryoablation procedure of the mitral isthmus is considered to have occurred once an ArcticLine cryoapplication at the mitral isthmus begins. Only the first ArcticLine cryoablation procedure of the mitral isthmus per subject will be included.

12.4. Ancillary Objective #3

Estimate the percentage of patients with acute treatment success of the ArcticLine Catheter at the CTI in patients who underwent CTI ablation with ArcticLine.

Endpoint Definition

Subjects must have confirmed bi-directional conduction block at the CTI line via periprocedural assessment at the completion of the cryoablation procedure to be considered an acute treatment success.

Analysis Methods

The percentage of acute CTI line treatment successes will be calculated as the number of CTI line procedures achieving success divided by the number of index ArcticLine cryoablation procedures where the CTI line was attempted. Exact methods will be used to construct a 95% confidence interval for the percentage.

Determination of Patients for Analysis

All subjects undergoing an ArcticLine cryoablation procedure of the CTI will be included. An ArcticLine cryoablation procedure of the CTI is considered to have occurred once an ArcticLine cryoapplication at the CTI begins. Only the first ArcticLine cryoablation procedure of the CTI per subject will be included.

12.5. Ancillary Objective #4

Characterize chronic treatment success of the ArcticLine Catheter in patients with demonstrated entrance block of all pulmonary veins.

Endpoint Definition

AF/AFL/AT episodes of at least 30 seconds duration from the end of the 90 day blanking period through the 6 month visit. Per section 8.6.1, the initiation of a new Class I or III antiarrhythmic medication or a Class I or III antiarrhythmic medication dose increase after the blanking period will be considered a chronic treatment failure. Also, a reablation for the treatment of recurrent AF/AT/AFL after the 90 day blanking period will be considered a chronic treatment failure.

Analysis Methods

Standard statistics will be used to summarize the percentage of patients without AF/AFL/AT and cumulative time spent in AF/AFL/AT as collected from the 6 month Holter data.

Note: Effectiveness data collected beyond the six month visit due to CIP Version 4 follow-up requirements will be adjudicated and included in the final report

Determination of Patients for Analysis

- All subjects undergoing an ArcticLine cryoablation procedure and who meet the following criteria will be included in the analysis:
 - Confirmed acute entrance block of all pulmonary veins
 - Confirmed acute posterior wall isolation (i.e. roof line and posterior wall line conduction block)
 - Confirmed acute bi-directional conduction block at the mitral isthmus, if applicable
 - Available 6 month Holter data
 - Note: An ArcticLine cryoablation procedure is considered to have occurred once the ArcticLine Catheter is introduced into the vasculature.
 - Note: For subjects who did not receive CTI ablation with ArcticLine Catheter, documented occurrence and treatment of typical right-sided cavotricuspid isthmus dependent atrial flutter during follow-up will not contribute to this endpoint.

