Inclusion/Exclusion Criteria	X							
Medical History	X							
Physical Exam	X							
AAD & Anticoagulation Medication Review	X		X	X	X	X	X	
Pregnancy Screen ³	X							
Arrhythmia Symptom Review	X			X	X	X	X	
NIHSS Assessment	X		X					X ⁶
Transthoracic Echocardiogram (TTE) ⁴	X							
Transesophageal Echocardiogram (TEE)	X							
12 Lead ECG	X		X		X	X	X	
Procedure Information		X						X
Post-ablation endoscopy ⁵		X						X
24 Hr Continuous Monitoring with Holter						X		

	Baseline	Procedure	Discharge	1 week ¹	3 month ²	6 month ²	Unscheduled	Repeat Ablation
Patient Activated Ambulatory ECG Monitor					Monthly and symptomatic episodes			
Adverse Events	As they occur							
Device Deficiencies	As they occur							
Study Deviations	As they occur							

Notes:
 
¹Phone visit and/or office visit with Nurse Coordinator
 
²Multiple modes of data collections may be employed to support the collection of required visit data at the 3 and 6 month visits such as: In office patient clinic visit, direct to patient contact (i.e. telephone, email, mail contact, etc.), and remote technology transmissions/uploads.
 
³Female subjects of child bearing potential only
 
⁴Only required if data not available from within 6 months prior to consent date
 
⁵Post-ablation endoscopy is required post-ablation, prior to discharge, only if the subject's esophageal temperature drops below 15 degrees C at any time during the study procedure.
 
⁶For repeat ablations using ArcticLine Catheter, NIHSS will be completed at baseline and discharge.
								
Safety Assessments	
Clinical Events Committee:
 
An independent committee comprised of electrophysiologists not participating in the study will review and adjudicate all adverse events as well as all deaths for subjects participating in the study.
							
Statistics	
No formal hypotheses for this study:
 
 • Data will be reported as collected and no imputation will be performed for missing or incomplete observations. • Analyses are planned at the following time points: 
 ○ After completion of the 15 subject index procedures and 1 week follow-up visit ○ After all subjects have completed follow-up visits through at least the 6 month follow-up visit and have been exited from the study 							

3. Introduction

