8.8.3. Six Month Visit

- Review medications
- Adverse event assessment
- Review symptoms suggestive of recurrent AF/AT/AFL
- 12 lead ECG
- 24-hour continuous monitoring with Holter
- Collect or ensure return of ambulatory monitoring equipment

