8.8.5. Holter and Patient Activated Ambulatory ECG Monitoring

Market-released Holters will be distributed by a core lab to centers after activation has occurred. All subjects will wear a Holter in conjunction with their 6 month visit. Holters will be sent to the core lab after they have been worn by the subject. The core lab will be responsible for adjudication of atrial arrhythmias. The core lab will manage maintenance, calibration and tracking of the Holters.

Market-released Patient Activated Ambulatory ECG Monitors will be distributed by a core lab to centers after activation has occurred. All subjects will transmit monthly and symptomatic ECGs following their 3 month visit. The monitors will be returned to the core lab at the end of the study. The core lab will be responsible for adjudication of atrial arrhythmias. The core lab will manage maintenance, calibration and tracking of the monitors.

8.8.6. 12 Lead Electrocardiograms

All 12 lead ECGs will be sent to the core lab. The core lab will be responsible for adjudication of atrial arrhythmias. Copies of additional source documents may be requested.

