The probability of a subject achieving effectiveness success at 6 months (182 days) will be estimated using survival analysis (the Kaplan-Meier method). The standard error will be approximated using Greenwood's formula. A two-sided 95% log-log confidence interval for the probability will be constructed.

For every treated subject, day 0 is defined as the day of the index ArcticLine procedure. For subjects without treatment failure through 6 months, those subjects will be censored at the last rhythm monitoring assessment (either in person monitoring at a visit via ECG/Holter, or through ambulatory ECG/transtelephonic monitoring). If a subject without a treatment failure is lost to follow-up, the censoring date will be set to the last date of rhythm monitoring that produced an interpretable rhythm; the date of capture/recording for a rhythm that the core lab was unable to interpret would not count.

For the AF/AT/AFL component of the endpoint, if documentation resulted from rhythm monitoring occurring at the 6-month visit within the 6-month visit window, the date of recurrence will be set to 182

days from the study ablation procedure so that these events will be counted as treatment failures in the 6-month Kaplan-Meier analysis.

Additionally, as stated in the CIP, standard statistics will be used to summarize the percentage of patients without AF/AFL/AT and cumulative time spent in AF/AFL/AT as collected from the 6 month Holter data. Listings will be provided for any data collected relevant to this objective that occurred after 6 months, due to CIP v5 follow-up requirements.

Determination of Subjects for Analysis

- All ArcticLine treated subjects who meet the following criteria will be included in the analysis:
 - o Confirmed acute entrance block of all pulmonary veins
 - o Confirmed acute posterior wall isolation (i.e. roof line and posterior wallline conduction block)
 - o Confirmed acute bi-directional conduction block at the mitral isthmus, if applicable
 - o Confirmed acute bi-directional conduction block at the CTI, if applicable
 - o Available 6 month Holter data (only required for description of Holter times, but not necessary for inclusion in Kaplan-Meier analysis)

7.27 Ancillary Objective 5

Estimate the incidence of ArcticLine Catheter-related and ArcticLine cryoablation procedure related serious adverse events (SAE) through the 6 month visit.

Ancillary Endpoint #5

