7.4 Handling of Missing, Unused, and Spurious Data and Dropouts

Subjects who (A) exit the study prior to completion of a phone conversation or follow-up visit 7 or more days after the index procedure and (B) do not have a primary safety event on or before discharge from the index ablation will be considered as missing for the primary endpoint analysis, on grounds that the assessment of the endpoint is incomplete. Subjects with early exits occurring after the one-week phone call will still be included, however: after 7 days post-index ablation, only the atrioesophageal fistula component, which occurs in less than one in 10,000 cryoballoon ablations¹, counts toward the primary endpoint. Therefore, the likely impact of failing to observe new occurrences of the primary endpoint in subjects not followed past one week is negligible. No effort to statistically impute missing data will be made for the primary endpoint or any ancillary endpoints; all such analyses will be "complete cases" and assume that observed missingness occurs completely at random with respect to the outcome.

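### Holter arrhythmia time is summarised without adjustment for analysable recording time, so a recording with fewer than 24 readable hours can understate burden

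*Protocol*

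**What the plan says.** The recording is planned once, at the six month visit, as "24-hour continuous monitoring with Holter" (Protocol 8.8.3). Protocol 12.5 reports from it "cumulative time spent in AF/AFL/AT as collected from the 6 month Holter data", together with the percentage of patients free of arrhythmia. SAP 7.26 keeps this: "standard statistics will be used to summarize the percentage of patients without AF/AFL/AT and cumulative time spent in AF/AFL/AT".

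The condition for entering the Holter summary is that a recording exists. The SAP lists it as "Available 6 month Holter data (only required for description of Holter times, but not necessary for inclusion in Kaplan-Meier analysis". No minimum duration is attached.

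On incomplete data, the Statistics row of the protocol synopsis says "Data will be reported as collected and no imputation will be performed for missing or incomplete observations", and SAP 7.4 says "No effort to statistically impute missing data will be made for the primary endpoint or any ancillary endpoints". SAP 7.1.2 refers the handling of rhythm monitoring deviations for this endpoint to the Ancillary Objective 4 section. The only rule on recording quality there concerns Kaplan-Meier censoring for subjects lost to follow-up: "the censoring date will be set to the last date of rhythm monitoring that produced an interpretable rhythm". It is not applied to the Holter summary.

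**The concern.** Absolute time in arrhythmia depends on two things: how much arrhythmia the subject had and how many hours could be read. Followed as written, the plan averages recordings of unequal length as if they were equal. A subject in AF throughout a Holter with 12 readable hours contributes 12 h; the same rhythm on a full recording contributes 24 h. Eligible subjects have had continuous AF lasting beyond 7 days, so a recurrence that fills the whole recording is plausible. In that case cumulative time simply measures recording length.

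The companion percentage is exposed in another way. A short recording without arrhythmia counts the same as a full one, and nothing in the planned output would show the difference.

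At stake is the interpretability of a descriptive summary. It is, however, the only analysis method that Protocol 12.5 gives for this objective; the SAP added the Kaplan-Meier analysis.

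**Working it through.** The plan states no figure for Holter burden, so there is none to reproduce.

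**Inputs**
- Planned recording length: 24 h (Protocol 8.8.3).
- Subjects: at most 15 Holters, from about 15 treated subjects (SAP 6).
- Analysable hours h: not in the documents. Assumed range 12 to 22 h.
- Unreadable time is assumed to count as no arrhythmia, and lost time to be unrelated to rhythm.

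**Per subject.** If the true share of time in arrhythmia is b, the expected cumulative time is b × h, against b × 24 on a full recording. The relative shortfall is 1 - (b × h)/(b × 24) = 1 - h/24, whatever b is.

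| Analysable hours | 1 - h/24 |
|---|---|
| 24 | 0% |
| 22 | 8% |
| 20 | 17% |
| 18 | 25% |
| 16 | 33% |
| 12 | 50% |

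This applies only to subjects with arrhythmia. A subject in sinus rhythm contributes zero either way.

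**Cohort mean.** If k of 15 recordings have h readable hours and burden is unrelated to length, the mean falls by (k/15) × (1 - h/24):
- 1 of 15 at 12 h: (1/15) × 0.50 = 3.3%
- 3 of 15 at 18 h: (3/15) × 0.25 = 5.0%
- 3 of 15 at 12 h: (3/15) × 0.50 = 10.0%

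The effect is larger if the short recording belongs to a subject in AF. As an illustration, suppose 2 of 15 are in continuous AF and the rest have none. With full recordings the mean is 48/15 = 3.2 h. If one of the two has 12 readable hours, it is 36/15 = 2.4 h, which is 25% lower. The mean share of analysable time is 2/15 = 13.3% in both cases.

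**Does the share repair it?** A simulation took 100,000 recordings per value of h. Each had one episode lasting between 0.5 and 24 h, placed at random around the clock.

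| h | True mean | Mean cumulative time | Share × 24 |
|---|---|---|---|
| 12 | 12.25 h | 6.11 h | 12.22 h |
| 20 | 12.25 h | 10.21 h | 12.26 h |

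The share recovers the true mean. It does so on average only: at 12 h, about half of the individual shares lay above the true value.

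The share does not repair missed detection. In the same simulation, an episode of at least 30 seconds was seen in 88% of recordings at 12 h and 99% at 20 h.

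**The case against.** The strongest reply is that recording length is fixed by design. When every Holter gives 24 readable hours, time and percentage of time differ only by a constant. Nothing in the documents says that short recordings are expected, and the values of h above are assumptions. This stands, and it makes the point conditional.

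The documents also speak of time without forbidding a percentage, and the SAP says that it does not limit further analysis. That permits the better summary but does not plan it.

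Other provisions help in part. For Holter data, "The core lab will be responsible for adjudication of atrial arrhythmias". Protocol 8.11 requires deviations to be recorded on the eCRF and exempts only missed ambulatory transmissions; SAP 7.1.2 lists deviations. A materially short wear should therefore come to light. Signal lost to artefact within a full-length wear would not, and neither route adjusts the summary.

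A reader might infer that the plan's measure is biased in favour of the device. The documents do not support that. The downward direction requires unreadable time to count as no arrhythmia. Artefact misread as AF, or a recording longer than 24 h, would push absolute time upwards.

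A reader might also infer that short clean recordings should be excluded below a minimum duration. The documents offer no basis for a cut-off. SAP version 3 states that all procedures are complete, so a threshold would come late, and it could remove subjects from at most 15.

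**Conclusion.** The point holds as a minor, inexpensive improvement. Both documents summarise absolute time with no adjustment for analysable time. Where a Holter falls short and unreadable time counts as no arrhythmia, that subject's figure is understated on average by 1 - h/24, over an assumed range of 8% to 50%. The corresponding effect on the cohort mean is about 3% with one 12 h recording among 15 and 10% with three, if burden is unrelated to length. It is zero if all recordings are full.

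It would be wrong to conclude that the chronic success estimate is distorted by this measure. The SAP's Kaplan-Meier analysis counts any AF/AFL/AT episode of at least 30 seconds as failure, so the subject with 12 readable hours of AF fails regardless. It also draws on ECG and ambulatory monitoring, does not require a Holter, and makes no use of time in arrhythmia. No hypothesis test depends on the Holter summary.

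**What to change.** In SAP 7.26:
- Report burden as time in AF/AFL/AT divided by analysable Holter time, in percent, beside the cumulative time already planned.
- List analysable hours per subject next to the arrhythmia-free result, so that short clean recordings can be seen.
- State that any AF/AFL/AT seen on a short recording still counts. Set no exclusion threshold.

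The cost is one derived variable and one listing column. SAP 7.8 allows the change through a new SAP version or as an explained deviation in the final report. There are two limits. The core lab must report analysable duration, which the documents do not confirm. And the share is unbiased only if lost time is unrelated to rhythm, which is why the hours should be listed and the cumulative time kept.
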